### **Comprehensive physical examination**

Each protocol-specified organ or body system for the comprehensive physical examination will be summarized for the Safety population by a shift table presenting the number and the percentage of patients in each bivariate category (Initial Screening Visit versus Day 14) with regards to Investigator’s interpretation (normal, abnormal NCS, abnormal CS, not done, and missing) by treatment group.

The results of targeted physical examination will be only listed.

### **Body weight**

Body weight will be summarized for the Safety population by treatment group at each applicable visit (Initial Screening Visit, Day 0, Day 7 and Day 14) by descriptive statistics (n, mean, SD, median, and range). In addition, at each visit after baseline, change from baseline will be calculated and summarized by descriptive statistics (n, mean, SD, median, and range). Baseline will be Day 0 if available, otherwise, the Initial Screening Visit assessment will be used.

A comparison between treatment groups with an ANCOVA model, with change from baseline to Day 14 as dependent variable, treatment as fixed effect and baseline as covariate. A LOCF method of imputation will be applied for missing values. The number of patients and the number of patients considered in the model will be provided by treatment. P-values of the fixed effects and covariates will also be presented. The adjusted means for treatments and the relative 95% CIs will be presented. The difference between the adjusted means of the three treatment groups will be calculated with the relative 95% CI and p value.

### **Vital signs other than BP**

Pulse rate (beats/min), respiration rate (breaths/min), and oral body temperature (degrees Celsius) will be summarized for the Safety population by treatment group at each applicable visit (Initial Screening Visit, Day 0, Day 7, Day 14, and Day 28) by descriptive statistics (n, mean, SD, median, and range). In addition, at each visit after baseline, change from baseline will be calculated and summarized by descriptive statistics (n, mean, SD, median, and range). Baseline will be Day 0 if available, otherwise, the Initial Screening Visit assessment will be used.

### **Vital signs - BP**

Clinic visit average resting SBP and DBP (mmHg) will be summarized for the Safety population by treatment group at each applicable visit (Initial Screening Visit, Day 0, Day 7, Day 14, and Day 28) by descriptive statistics (n, mean, SD, median, and range). In addition, at each visit after baseline, change from baseline will be calculated and summarized by descriptive statistics (n, mean, SD, median, and range). Baseline will be Day 0 if available, otherwise, the Initial Screening Visit assessment will be used.

For each variable (average resting SBP and DBP) a comparison between treatment groups will be performed with an ANCOVA model with change from baseline to Day 14 as dependent variable, treatment as fixed effect and baseline as covariate. A LOCF method of imputation will be applied for missing values. In the event there is no Day 14 measurement, the Day 7 measurement will be carried forward. Baseline measurement is Day 0 (prior to study drug administration); however, in the event the Day 0 measurement is missing, the Initial Screening Visit measurement will be carried forward. The number of patients and the number of patients considered in the model will be provided by treatment. The adjusted means for treatments and the relative 95% CIs and p values will be presented. The difference between the adjusted means of the three treatment groups will be calculated with the relative 95% CI and p-value.

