
Statistical Methods for Secondary Efficacy Analysis:
	
A serial gatekeeping strategy will be used to evaluate the effect of amlodipine tablets (10 mg) and celecoxib capsules (200 mg) given together on secondary efficacy endpoints. If and only if the primary blood pressure efficacy endpoint is statistically achieved, a secondary hierarchical analysis will be used to evaluate the endpoints listed below, and will only proceed to the next endpoint in the list if the alpha is met for the prior analyses.
 
 1. Difference in mean change in body weight from baseline (Day 0) to Day 14 (or Day 7 for subjects withdrawn from treatment at Day 7) between treatment arms [amlodipine tablets (10 mg) and celecoxib capsules (200 mg) given together (arm 1), amlodipine tablets (10 mg) given alone (with matched celecoxib placebo) (arm 2), and placebo (arm 3)]; 2. Difference in the mean reduction in SBP_{24h} from the baseline (Day -1 to Day 0) ABPM measurement to the Day 13 to Day 14 ABPM measurement (or to the Day 6 to Day 7 ABPM measurement for subjects withdrawn from treatment at Day 7) between subjects treated with amlodipine tablets (10 mg) and celecoxib capsules (200 mg) given together (arm 1) and amlodipine tablets (10 mg) given alone (with matched celecoxib placebo) (arm 2); 3. Difference in the mean reduction in DBP_{24h} from the baseline (Day -1 to Day 0) ABPM measurement to the Day 13 to Day 14 ABPM measurement (or to the Day 6 to Day 7 ABPM measurement for subjects withdrawn from treatment at Day 7) between subjects treated with amlodipine tablets (10 mg) and celecoxib capsules (200 mg) given together (arm 1) and amlodipine tablets (10 mg) given alone (with matched celecoxib placebo) (arm 2); 4. Difference in the mean change in creatinine clearance from baseline (Day 0) to Day 14 (or Day 7 for subjects withdrawn from treatment at Day 7) between subjects treated with amlodipine tablets (10 mg) and celecoxib capsules (200 mg) given together (arm 1) and amlodipine tablets (10 mg) given alone (with matched celecoxib placebo) (arm 2). 
Analysis of variance (ANOVA) will be utilized to compare body weight changes among the three treatment arms. Change in body weight will be the response with treatment arm

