Study Day 28: Subjects will return to clinic on Day 28 for their final study visit (follow-up visit). The diary will be reviewed for any concomitant medications taken since the prior visit. Subjects will be solicited for history of TEAEs since the previous visit. A targeted physical examination will be performed and vital signs will be measured. For subjects whose study drugs are discontinued at Day 7, this follow-up visit will still occur on Day 28 (i.e., these subjects will return to the clinic for both the Day 14 and Day 28 visits).

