5. Subjects will be provided back their diary and instructed to record any concomitant medications taken and details of study drug administration;
6. Instruct subjects to return to the clinic in 6 days (on the morning of Day 13), and to bring the completed diary and study drug containers with any unused study drug.

If during the Day 7 visit, the subject's BP is too elevated for them to continue safely in the study (i.e., SBP_{24h} > 169 mmHg and/or DBP_{24h} > 110 mmHg), blood will be drawn for renal profile testing (see Section 8.5). The subject will be instructed to cease taking study drugs, instructed to resume taking their prescribed BP medication as directed by the study doctor or general practitioner, given back their diary and instructed to record any concomitant medications taken between visits, and instructed to return to the clinic in 7 days (Day 14).

6.5 Study Day 13

Subjects will return to clinic on the morning of Day 13 (except for those discontinued from study drug due to excessive hypertension or other safety reasons at Day 7) and will undergo the following procedures:

1. Solicit history of TEAEs since the previous visit;
2. Review diary for details of study drug administration and concomitant medications since the previous visit;
3. Collect study drug containers and count and record any unused study drug;
4. Provide subjects with an ABPM, instruct in its use, and check the positioning of the ABPM.

Following the placement of the ABPM, the subjects will be administered their Day 13 dose of study drugs (final dose) in the clinic. Prior to leaving the clinic, the following procedures will be performed:

1. Instruct subjects to wear the APBM at all times for the next 25 hours;
2. Subjects will be given back their diary and instructed to record any concomitant medications taken between visits;
3. Instruct subjects to return to clinic the following day (on the morning of Day 14), and to bring the completed diary to the clinic.

6.6 Study Day 14

Subjects will return to clinic on the morning of Day 14. The following evaluations will be performed:

1. Solicit history of TEAEs since the previous visit;
2. Review diary for details of concomitant medications since the previous visit;
3. Comprehensive physical examination (see Section 8.2);
4. Body weight while only wearing underwear and a light gown;
5. Vital signs (BP, pulse rate, respiration rate, and oral body temperature);

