8.3 Vital Signs

Vital sign measurements (BP, pulse rate, respiration rate, and oral body temperature) will be collected on the days and times noted in the Schedule of Events (Appendix A). Vital signs will be taken with the subject in the sitting position after 5 minutes of rest, except for at the initial screening visit, where vital signs will be taken with the subject in the supine position after at least 10 minutes of rest with minimal interaction.

Measurements of BP made when subjects are at the Investigational Site as part of their clinic visits will be made using the standard American Heart Association criteria (Chobanian, 2003). This will require the following technique be utilized:

1. Clinic visit BP measurements will be taken at the initial screening visit, in the morning on Days 0, 7, and 14, and at the follow-up visit (Day 28). On Day 0, the BP measurements will be taken in the morning prior to the first dose of study drugs. On Day 7, the subject will self-administer their study drugs at home prior to coming to the clinic, and therefore, the BP measurements will be taken after the subject has taken their daily dose of study drugs;

2. A determination will be made as to which upper extremity has the greater BP;
3. Prior to taking the subject's BP, the subject will rest in the sitting position for a period of 5 minutes, except for at the initial Screening visit, where BP measurements will be taken with the subject in the supine position after at least 10 minutes of rest with minimal interaction;
4. At the completion of the rest period, three readings will be taken. There will be a one minute interval between each measurement;
5. The subject's recorded BP will be an average of the three recordings taken over approximately three minutes.
6. At the initial screening visit (Day -10 to -14), three readings will be taken on each arm, as described. The averages for each arm will be calculated. The arm with the higher average systolic BP will be used for all further BP measurements including ABPM measurements.

The continuous recording of BP by ABPM (Section 7.1) at Day -1 to Day 0, Day 6 to Day 7, and Day 13 to Day 14, will serve a dual function as both the official BP values for all efficacy determinations and calculations and an additional BP assessment for safety.

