**h. Vital signs**

Descriptive statistics [n, mean, standard deviation (SD), median and range] will be added for the change from baseline at each visit (Days 7, 14, and 28) for each vital sign (clinic visit resting SBP and DBP, pulse rate, respiration rate, and oral body temperature) for the safety population. The protocol-specified comparisons among treatment arms using ANCOVA will be limited to SBP and DBP (and not performed for pulse rate, respiration rate, and oral body temperature). Further, the resting SBP and DBP ANCOVA comparisons will be limited to the change from baseline to Day 14 (and not evaluated for the change from baseline to Days 7 or 28) since the effect would be more limited after only 7 days, and since subjects would have been off study drugs for 14 days at Day 28. The LOCF method of imputation will be applied for missing values.

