### 2.3. Primary Endpoint(s)

#### Efficacy:

The primary efficacy endpoint for this trial is the difference in the mean reduction in SBPday from the baseline (Day -1 to Day 0) ABPM measurement to the final (Day 13 to Day 14) ABPM measurement, where a subject completes the 14-day treatment plan, or to the Day 6 to Day 7 ABPM measurement, where a subject is withdrawn from treatment at Day 7, between subjects treated with amlodipine tablets (10 mg) and celecoxib capsules (200 mg) given together (arm 1) and amlodipine tablets (10 mg) given alone (i.e., with matched celecoxib placebo) (arm 2).

The primary efficacy endpoint is that the lower limits of the 97.5% one-sided CI for the difference in SBPday reduction in treatment arm 1 and 50% of the mean reduction in treatment arm 2 is less than 0. Note, as detailed in section 6.7, because the preferred outcome is a larger reduction, a negative value indicates a larger reduction in arm 1 as compared to arm 2.

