## 7. Statistical Methodology

### 7.1. Handling of Missing Data

For ITT and mITT population, if at the time of the Day 7 clinic visit subjects have a too elevated BP to be able to continue safely in the study (i.e., SBP24h > 169 mmHg or DBP24h > 110 mmHg), blood will be drawn for renal profile testing, the study drug will be discontinued and the subjects will be instructed to resume taking their prescribed BP medication as directed by the study doctor or general practitioner. In case of missing data, LOCF techniques will be used as follows:

1. ITT population: LOCF from baseline (Day 0)
2. mITT population: LOCF from Day 6

Using this method, the end of study measurement is either Baseline, Day 6 or Day 13.

No specific analysis for withdrawn patients will be presented.

The number of patients with missing data will be presented under the “Missing” category, if present. Missing values will be included in the denominator count when computing percentages.

When continuous data are being summarized, only the non-missing values will be evaluated for computing summary statistics.

Missing or incomplete data will be treated as described in sections 5, 6.4, 6.5, 7.1, 7.9, 7.10. Other critical missing data will be discussed prior to treatment unblinding, if any. Decisions will be taken during the data review and will be fully documented in the Data Review Report.

The LOCF method of imputation will be applied for missing values in all ANCOVA models. This method will not be applied to the descriptive statistics.

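### The Day 14 clinic-BP comparison scores subjects stopped at Day 7 for high BP on off-drug, rescue-instructed readings, with no on-drug between-arm test beside it and no count of BP-limit stops (minor)

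*SAP*

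**What the plan says.** **Stopping and return.** Protocol 6.4 (Study Day 7) says of a subject over either 24-hour limit: "The subject will be instructed to cease taking study drugs, instructed to resume taking their prescribed BP medication". Protocol 3 (Study Day 28) adds that "these subjects will return to the clinic for both the Day 14 and Day 28 visits". Protocol 4.3 qualifies this: after withdrawal, the Day 14 evaluations are done if feasible. Protocol 8.3 sets the clinic readings: "Clinic visit BP measurements will be taken at the initial screening visit, in the morning on Days 0, 7, and 14". On Day 7 they follow that morning's dose.

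**The test.** SAP 7.9 (Vital signs - BP) fits an ANCOVA to the change in clinic SBP and DBP from baseline to Day 14 and reports differences among all three arms. Its imputation rule is "In the event there is no Day 14 measurement, the Day 7 measurement will be carried forward". SAP 1.3.9 h limits the test to Day 14. It sets Day 28 aside "since subjects would have been off study drugs for 14 days at Day 28".

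**Rules elsewhere for the same subjects.** The primary endpoint (SAP 2.3) runs to Day 13-14, "or to the Day 6 to Day 7 ABPM measurement, where a subject is withdrawn from treatment at Day 7". The protocol synopsis, for body weight and creatinine clearance, takes Day 14, "or Day 7 for subjects withdrawn from treatment at Day 7".

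**Reporting of withdrawals.** SAP 7.1 states: "No specific analysis for withdrawn patients will be presented". SAP 7.4 breaks discontinuations into six reasons, none of which is elevated BP.

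**The concern.** The trigger for using Day 7 is a missing Day 14 reading. Stopping study drug or starting rescue does not trigger it. A subject whose BP went over the safety limit on treatment, and who then follows the protocol, contributes a Day 14 value taken after a week off study drug with other BP medication resumed. The model credits that value to the assigned arm. The plan avoids this for the primary endpoint and, in the synopsis, for weight and creatinine clearance.

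The direction depends on where the stops fall. A stop in arm 1 makes the combination look better controlled than it was. A stop on placebo lowers placebo BP and makes both amlodipine arms look less effective against it. A reader could not tell from the planned summary tables how many such subjects there were, because no row isolates the reason. SAP 1.1 cites agreement between ABPM and clinic readings in the previous trial as evidence that the effect is real, so this comparison may be read as corroboration as well as safety.

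**Working it through.** The documents give no sample size, SD or power for this ANCOVA, so there is no planned figure to reproduce. The check has three parts.

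**1. Is the Day 14 reading off drug?** The last dose is on the morning of Day 7, so Day 14 is about 7 × 24 = 168 h later. Amlodipine's terminal half-life is about 30-50 h (Protocol Appendix F, label section 12.3). Half-lives elapsed: 168/50 = 3.4 to 168/30 = 5.6. Fraction left: 0.5^3.36 = 0.10 to 0.5^5.6 = 0.02. The reading is essentially off drug.

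**2. How many stops?** The number is not in the documents. Assumptions: the previous study's SBPday changes (Protocol 1) stand in for the Day 7 change in SBP24h; tails are normal; every subject in a column has the same baseline SBP24h; only the systolic limit counts. Mean change and SD: arm 1 −10.6, 9.2; arm 2 −8.8, 8.1; placebo −2.1, 8.2.

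P(stop) = 1 − Φ((169 − baseline − mean change)/SD).

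Arm sizes: 105 at 3:3:1 gives 45/45/15. SAP 3.2 reports a realised ratio of 6:6:1, and 105/13 gives about 8 on placebo. I keep 45 for the amlodipine arms throughout.

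| Baseline SBP24h | 150 | 155 | 160 |
|---|---|---|---|
| P(stop), arm 1 | 0.00065 | 0.00375 | 0.01657 |
| P(stop), arm 2 | 0.00030 | 0.00244 | 0.01399 |
| P(stop), placebo | 0.00504 | 0.02480 | 0.08792 |
| Expected stops, arm 1 (n=45) | 0.03 | 0.17 | 0.75 |
| Expected stops, arm 2 (n=45) | 0.01 | 0.11 | 0.63 |
| Expected stops, placebo n=15 | 0.08 | 0.37 | 1.32 |
| Expected stops, placebo n=8 | 0.04 | 0.20 | 0.70 |

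Per-subject risk on placebo is 5.3 to 7.8 times that in arm 1. Three or more stops in arm 1 has probability 0.00066 at 155 and 0.0385 at 160. Putting every subject at 160 is extreme. A simulation with mean baselines of 145 to 155 mmHg (SD 8-9, restricted to above 135 and up to 169) gives 0.1 to 0.7 expected stops per amlodipine arm and 0.2 to 1.0 of 15 on placebo. A likely total of 0 to 2 is reasonable.

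**3. What does one stop do?** Shift in arm mean = (rise − rescued change)/n. The rise just reaches 169, so it is 19, 14 or 9 mmHg. The rescued change is taken as 0 or −8.8. Clinic BP is assumed to behave like ABPM.

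- n=45: 9/45 = 0.20 to (19 + 8.8)/45 = 0.62 mmHg
- n=15: 9/15 = 0.60 to 27.8/15 = 1.85 mmHg
- n=8: 9/8 = 1.13 to 27.8/8 = 3.48 mmHg

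For scale, the standard errors are:

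- Arm 1 minus arm 2: √(9.2²/45 + 8.1²/45) = 1.83
- Arm 1 minus placebo, n=15: √(9.2²/45 + 8.2²/15) = 2.52
- Arm 1 minus placebo, n=8: √(9.2²/45 + 8.2²/8) = 3.21

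Example: one placebo stop, n=8, baseline 155, rescued change −8.8. Placebo mean on last on-drug values: (7 × −2.1 + 14)/8 = −0.09. As planned: (7 × −2.1 − 8.8)/8 = −2.94. Arm 1 minus placebo is then −10.51 and −7.66 respectively.

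**The case against.** The strongest reply is that most of the information is already there. SAP 7.9 summarises Day 7 clinic BP and its change by arm, and that reading is on drug. The next subsection does the same for Day 6-7 ABPM. SAP 1.3.4 and 7.10 test arms 1 and 2 against placebo on SBPday, SBP24h and DBP24h, carrying Day 6-7 forward for early withdrawals. Protocol 7.1 makes ABPM the official BP for efficacy. SAP 7.3 lists all CRF data, so individual stops can be traced. SAP 7.4 counts treatment completers, and a Day 7 stop has taken 8 of 14 doses (57%), so falls in the under-75% compliance category. A stop recorded as a hypertension TEAE would appear by preferred term and arm. All of this stands. A reader might infer that on-drug clinic BP goes unreported, and the documents do not support that. Only the on-drug between-arm test is missing.

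Scoring an attended visit under the assigned arm is also a legitimate as-collected safety analysis. The safety ANCOVA for body weight in SAP 7.9 likewise imputes only missing values, and the contrasting rules are efficacy rules. At Day 28 every subject is off drug, whereas at Day 14 only stopped subjects are, so the Day 28 rationale is not a direct contradiction. That is why the planned analysis should stay.

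The sizes are modest too. With the assumed baseline of 155, the chance of no stop in any arm is 52% (placebo n=15) to 62% (n=8). At least one placebo stop at n=8 has probability 1 − 0.9752^8 = 18%. In the example, −7.66/3.21 is z = 2.4 and −10.51/3.21 is z = 3.3, so the conclusion at 0.05 is the same.

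What remains is that the one reported between-arm test of clinic BP can mix on-drug and rescued readings unannounced, and no summary row isolates BP-limit stops.

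**Conclusion.** The point holds as a minor one. An attended Day 14 visit after a Day 7 BP stop enters the clinic-BP ANCOVA as an off-drug, rescue-instructed value. If Day 14 is missed, the on-drug Day 7 value is used and the issue disappears. Resumption of BP medication is instructed, not guaranteed.

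The arm 1 versus arm 2 result is unlikely to change: 0.2 to 0.6 mmHg per stop against an SE of 1.8, or 15 × √(2/45) = 3.2 if clinic-BP SD is as high as 15. The placebo contrasts are more exposed because that arm is small and its per-subject risk is highest: about 1 to 3.5 mmHg per stop at n=8, against an SE of 3.2. These figures rest on assumed baselines, on borrowed ABPM changes and SDs, and on a placebo arm of about 8. The actual number of stops is not in the documents.

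Two stronger readings go too far. A reader might infer that the plan hides harm from the combination. The direction depends on which arm has stops, and the arm at highest per-subject risk is placebo, where the distortion works against amlodipine. A reader might also infer that the primary result is affected. It is not, because it uses the Day 6-7 ABPM for subjects withdrawn at Day 7.

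**What to change.** Keep the Day 14 ANCOVA as planned. In SAP 7.9 (Vital signs - BP), add for SBP and DBP:

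*A sensitivity ANCOVA, added after unblinding, will be reported beside the planned one. Day 7 clinic BP replaces Day 14 for subjects withdrawn from study drug at Day 7, or who resumed BP medication before the Day 14 reading. Subjects who only missed a late dose keep their Day 14 value.*

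The last sentence matters. A subject whose last dose was on Day 12 is about 48 h post-dose at Day 14, or 48/50 = 1.0 to 48/30 = 1.6 half-lives, with no instructed rescue, so that near-on-drug value should be kept. A subject whose Day 7 reading is itself off drug or after resumption should be left out of this run and counted by arm.

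In SAP 7.4, add one by-arm row: *study drug stopped because SBP24h > 169 or DBP24h > 110 mmHg*. If there were none, the row settles the question.

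The cost is one more model run each for SBP and DBP and one table row, from data already collected (Day 7 clinic BP, withdrawal date and reason, concomitant medication). There are two downsides. SAP v4.0 is already a post-unblinding version (SAP 1.5), and this adds one more analysis to it. Also, Day 7 BP is a post-dose, one-week reading, whereas Day 14 is about 24 h after the last dose. The new run therefore supplements the planned one and does not replace it.
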